In the dose-expansion phase, 2 cohorts of approximately 10 subjects each will be examined in the dose-expansion phase at dose levels [REDACTED] every 7 days. The first 10 subjects enrolled into the dose-expansion phase will receive doses of MEDI-573 [REDACTED] every 7 days. The decision to continue enrollment of subjects into the lower [REDACTED] dose-expansion cohort will be based on pharmacodynamic assessments of tissue obtained from subjects pre- and post-exposure to MEDI-573 at the [REDACTED] level. In the event there is insufficient activity at the tissue level in the higher dose expansion cohort, the sponsor may halt dose-expansion and no additional subjects will be enrolled into the expansion phase. Enrollment in the dose-expansion phase can occur simultaneously with Cohorts 6 and 7.

In both the dose-escalation (Cohorts 1 through 5 only) and the dose-expansion phases of the study, in Cycle 2 and beyond, a dose can be delayed up to 7 days based on hematologic and nonhematologic toxicities, according to the conditions described in Section 3.5.5, but all 3 doses (Cohorts 1 through 5 and the dose expansion phase only) must be completed within the cycle in order for the cycle to be considered complete. Subjects in Cohorts 6 and 7 cannot have dose delays for hematologic or nonhematologic toxicities. Subjects who do not receive all required doses within a cycle will not advance to the next cycle and will be removed from treatment. Each new cycle will begin 7 days after the last dose of the previous cycle (Cohorts 1 through 5 and the dose expansion phase) or 21 days after the first dose of the previous cycle (Cohorts 6 and 7). For Cohorts 1 through 5 and the dose expansion phase, all visits during Cycle 2 and subsequent visits may occur in a ± 2 -day window to accommodate schedule changes, but doses of MEDI-573 must not occur more frequently than every 6 days. For Cohorts 6 and 7, all visits during Cycle 2 and subsequent visits may occur in a + 2-day window to accommodate schedule changes, but doses of MEDI-573 must not occur more frequently than every 21 days.

Subject Evaluation and Follow-up:

After informed consent has been obtained, screening evaluations will occur within 28 days prior to study entry and include the following evaluations: medical history; serum β human chorionic gonadotropin (β hCG) for women (unless surgically sterile or >1 year postmenopausal); complete physical examination (including height and weight); vital signs;

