Serum β hCG	X								
Urine β hCG		X				X			
MEDI-573 administration ^c		X				X			
Physical examination ^d	X	X				X		X	X
Height	X								
Weight	X	X				X			X
Vital signs ^e	X	X		X	X	X	X		X
ECG ^f	X	X ^g				X			X
Hematology ^h	X	X		X	X	X	X		X
Serum chemistry ⁱ	X	X		X	X	X	X		X
Urinalysis ^j	X	X				X			X

Table 3.6-2 Schedule of Subject Evaluations: Screening and Treatment Periods (Dose Escalation Cohorts 6 and 7 Only)

Evaluation	Screen ^a	Cycle 1				Cycle 2 and Every Cycle Thereafter		Every 2 Cycles	End of Treatment ^b
		Day 1	Day 2	Day 3	Day 8	Day 1	Day 8		
AE/SAE assessment	X	X		X	X	X	X	X	X
Concomitant medications	X	X		X	X	X	X	X	X
CT or MRI scans	X							X	X
Karnofsky performance status	X	X				X			X
MEDI-573 serum concentration ^k		X	X	X	X	X			X
Circulating tumor cells ^l	X					X			X
Anti-MEDI-573 antibodies ^m		X				X			
Blood biomarker analysis ⁿ		X	X	X	X	X			X
Whole blood RNA analysis	X								X
Archived tumor sample ^o	X								
Tumor biopsies ^p	X								

^a Screening evaluations must be performed within 28 days prior to first administration of MEDI-573.

^b This procedure does not need to be repeated if performed within 14 days of disease progression or treatment discontinuation

^c MEDI-573 will be administered as a 90-minute IV infusion once every 21 days.

^d Complete physical examination at Screening, after every 2 cycles, and at the end of treatment, and a physical examination for the purpose of disease evaluation at screening and on Day 1 of each cycle.

^e On days of MEDI-573 administration, vital signs will be recorded immediately prior to infusion, at every 15 minutes during infusion \pm 5 minutes, at completion of infusion (\pm 5 minutes) and 30 and 60 minutes after completion of the infusion \pm 5 minutes.

Table 3.6-2 Schedule of Subject Evaluations: Screening and Treatment Periods (Dose Escalation Cohorts 6 and 7 Only)

Evaluation	Screen ^a	Cycle 1				Cycle 2 and Every Cycle Thereafter		Every 2 Cycles	End of Treatment ^b
		Day 1	Day 2	Day 3	Day 8	Day 1	Day 8		

^f ECG equipment (with instant print-out and electronic transmission capabilities) and training will be provided to all study sites. All ECGs performed during the study will be obtained in triplicate (ie, 3 ECGs will be obtained within a 5 minute time interval). All ECGs should be done prior to PK draw for corresponding timepoints.

^g Prior to infusion and at completion of infusion (± 5 minutes), All ECGs should be done prior to PK draw for corresponding timepoints.

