^h Hematology laboratory parameters include complete blood count (CBC) with differential and platelet count. HgA1c is measured at screening and end of treatment.

ⁱ Serum chemistry includes AST/ALT, total bilirubin, creatinine (and creatinine clearance at Screening), alkaline phosphatase, sodium, potassium, chloride, phosphorous, calcium, glucose, albumin, magnesium, LDH; TSH will be measured at Day 1 of each new cycle and at the end of treatment.

^j Routine with microscopy

^k PK samples will be collected at the following timepoints: Cycle 1 Day 1, pre-infusion and immediately post completion of infusion (± 5 minutes); Day 2 at 24 hours post Day 1 infusion ± 2 hours; Day 3 at 48 hours post Day 1 infusion ± 2 hours; Day 8; at Subsequent cycles Day 1 immediately prior to and post infusion; at the time of treatment discontinuation and 21 and 30 days after the last dose of MEDI-573

^l Sample collection for circulating tumor cells in blood should be done prior to MEDI-573 administration.

^m Sample collection for anti-MEDI-573 antibodies should be done pre dose (prior to MEDI-573 administration).

ⁿ Timepoints for biomarker collections are listed in Section 3.7.6.1. Insulin and GH are collected at one timepoint per visit. Tumor markers are collected as clinically indicated.

^o If an archived tumor sample is available and the subject provides consent, the sample is collected at screening only; Collect and ship per instructions in the Specimen Collection Manual.

^p Includes any biopsy tissue from intermediate timepoints as routine clinical management permits (optional).

Table 3.6-3 Schedule of Subject Evaluations: Follow-up Periods for All Subjects (Dose Escalation Cohorts 1 through 7 and the Expansion Phase)

Evaluations	Follow-up/Post-therapy		
	21 Days + 3 Days	30 Days + 3 Days	Every 3 Months ±2 Weeks
Physical examination		X	X ^a
Weight		X	
Vital signs		X	
ECG		X	
Hematology		X	
Serum chemistry (including TSH)		X	
Urinalysis		X	
Urine βhCG (women of childbearing potential only)		X	
AE/SAE assessment		X	
Concomitant medications		X	
CT or MRI scans			X ^a
Karnofsky performance status		X	X ^a
Subsequent anticancer therapy		X	X
Survival status			X
MEDI-573 serum concentration	X	X	X ^b
Anti-MEDI-573 antibodies		X	X ^b

Table 3.6-3 Schedule of Subject Evaluations: Follow-up Periods for All Subjects (Dose Escalation Cohorts 1 through 7 and the Expansion Phase)

Evaluations	Follow-up/Post-therapy		
	21 Days + 3 Days	30 Days + 3 Days	Every 3 Months ±2 Weeks

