3.7.5 Pharmacokinetic and Immunologic Evaluations

Blood samples for assessment of PK parameters of MEDI-573 and anti-MEDI-573 antibodies will be collected as described in [Table 3.6-1](#), [Table 3.6-2](#), and [Table 3.6-3](#). At Cycle 1 Day 1, serum for PK analysis will be collected immediately prior to infusion, immediately following infusion, and for subjects in Cohorts 1 through 5 and the expansion phase only, PK samples will also be collected 2 and 6 hours post infusion. Subjects in Cohorts 6 and 7 will not have a 2 or 6-hour post infusion PK collection. Additional PK samples will be collected during Cycle 1 on Day 2 at 24 hours post Day 1 infusion \pm 2 hours and Day 3 at 48 hours post Day 1 infusion \pm 2 hours, Day 8 and Day 15 pre-infusion and immediately after the infusion. Subsequently PK samples will be collected pre-infusion and immediately following infusion (\pm 5 minutes) of MEDI-573 every 7 days (ie, on Days 1, 8, and 15 of each cycle, Cohorts 1 through 5 and dose expansion phase) or every 21 days (ie, on Day 1 of each cycle, Cohorts 6 and 7), at the time of discontinuation of MEDI-573, and at 21 days, 30 days and 3 months post-therapy. Samples for anti-MEDI-573 antibodies will be collected at Screening and subsequently prior to each infusion of MEDI-573.

Details for collection, aliquoting, storage, and shipment of plasma samples for PK and IM evaluations are presented in the Specimen Collection Manual provided by the Sponsor.

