3.7.6 Pharmacodynamic Evaluations

3.7.6.1 Biomarker Analysis

Blood collection for assessment of biomarkers and other biological processes will be performed as described in [Table 3.6-1](#), [Table 3.6-2](#), and [Table 3.6-3](#).

Specific biomarkers may include free and bound IGF-1, IGF-2, and IGFBP levels, which will be evaluated by the Sponsor. Growth hormone, insulin, and tumor markers (when appropriate, such as prostate specific antigen [PSA] and cancer antigen 125 [CA 125]) will be drawn and evaluated at local clinical laboratories.

Details regarding blood sample collection for assessment of biomarkers are described in the Specimen Collection Manual provided by the Sponsor.

Growth hormone and insulin biomarkers will be collected at one timepoint per visit as described in [Table 3.6-1](#), [Table 3.6-2](#), and [Table 3.6-3](#). Tumor markers will be collected as clinically indicated. Samples for biomarker evaluations to be shipped to the sponsor will be collected at the following timepoints:

- Cycle 1 Day 1: pre-infusion
- Cycle 1 Day 1: end of infusion
- Cycle 1 Day 1: 2 hours post-infusion
- Cycle 1 Day 1; 6 hours post-infusion
- Cycle 1 Day 2: 24 hours post-Day 1 infusion
- Cycle 1 Day 3: 48 hours post-Day 1 infusion
- Cycle 1 Day 8: pre-infusion
- Cycle 1 Day 8: end of infusion
- Cycle 1 Day 15: pre-infusion
- Cycle 1 Day 15: end of infusion
- Cycle 2 and higher Days 1, 8 and 15: pre-infusion and end of infusion (Cohorts 1 through 5 and the expansion phase)
- Cycle 2 and higher Day 1 only (Cohorts 6 and 7)
- End of Treatment
- Day 21 post-therapy

- Day 30 post-therapy
- 3 months post-therapy

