4.10 Definitions of Dose-limiting Toxicities

Dose-limiting toxicities will be graded according to the NCI CTCAE V3.0 and will be assessed during the first cycle of treatment with MEDI-573 (Cycle 1, Day 1 through Cycle 1, Day 21).

A DLT is defined as:

- 1) Any Grade 3 or higher non-hematologic toxicity that occurs during the DLT assessment period where a cause other than the investigational product (such as disease progression or accident) cannot be reasonably justified with the following exceptions:
 - Grade < 4 serum-high glucose (fasting) with duration of < 24 hours.
 - Grade 3 fever (in the absence of neutropenia) defined as > 40.0°C (>104.0°F) that resolves to normal or baseline within 24 hours of treatment and is not considered an SAE; or
 - Grade 3 rigors/chills that respond to optimal therapy.
- 2) Any Grade 3 or higher hematologic toxicity that occurs during the DLT assessment period where a cause other than the investigational product (such as disease progression or accident) cannot be reasonably justified.

5 Statistical Considerations

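### Cohorts 6 and 7 have no scheduled safety laboratory test on Days 9 to 21 of the DLT window, and the schedule contradicts Sections 3.7.5 and 3.7.6.1 on Cycle 1 sampling

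*Protocol*

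**What the plan says.** **DLT period.** Section 4.10 assesses DLTs over "Cycle 1, Day 1 through Cycle 1, Day 21". Hematologic toxicity of Grade 3 or above counts, unless a cause other than the study drug can reasonably be justified. Non-hematologic toxicity of that grade also counts, with listed exceptions.

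**Visits for Cohorts 6 and 7.** Table 3.6-2, footnote c: "MEDI-573 will be administered as a 90-minute IV infusion once every 21 days". Cycle 1 has columns for Days 1, 2, 3 and 8. Hematology, chemistry and AE assessment are marked on Days 1, 3 and 8. In Section 3.6 the Cycle 1 Day 15 visit is restricted to Cohorts 1 to 5 and the expansion phase. Per the Study Abstract, Cycle 2 starts 21 days after the first dose, and only a later shift, of up to 2 days, is allowed.

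**Use of the window.** Under Section 4.9 item 2, no DLT in three subjects through 21 days opens the next cohort. For Cohort 7 the sponsor also weighs PK, pharmacodynamic, immunogenicity and safety data. Under Section 5.1 a subject in these cohorts is evaluable after one dose and 21 days of follow-up.

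**Sampling.** Table 3.6-2 footnote k takes PK from "Day 8; at Subsequent cycles Day 1 immediately prior to and post infusion", with no Day 15 sample. Section 3.7.5 lists Cycle 1 PK on "Day 8 and Day 15 pre-infusion and immediately after the infusion" without naming cohorts. Section 3.7.6.1, to which footnote n refers for biomarker times, lists "Cycle 1 Day 15: pre-infusion", also without naming cohorts. Section 3.7.5 further states: "Subjects in Cohorts 6 and 7 will not have a 2 or 6-hour post infusion PK collection".

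**The concern.** The DLT count is a primary safety result and drives the 3+3 decision. Grade 3 or 4 cytopenias and transaminase rises can be silent and are then found only by a blood test. The documents give reason to look for them. Section 1.5 reports anemia, thrombocytopenia and raised AST, each in at least 2 of the 17 subjects treated so far, and Section 1.2 cites Grade 3 and Grade 4 thrombocytopenia with antibodies against this pathway. As the schedule stands, a Cohort 6 subject can be evaluable and DLT-free with the last laboratory test on Day 8.

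The sampling conflicts matter for a different reason. The Cohort 7 decision draws on Cohort 6 PK and pharmacodynamics, and the OBED in Section 5.3 rests on circulating IGF data and PK/pharmacodynamic modeling. A site following Table 3.6-2 and a site following Section 3.7 would collect different data.

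**Working it through.** **1. Day count.** The protocol gives no visit-coverage figure. Its stated window, Day 1 through Day 21, is 21 days. Cycle 2 Day 1 in Cohorts 6 and 7 is Day 1 + 21 = Day 22, or at latest 22 + 2 = Day 24.

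| | Cohorts 6–7 | Cohorts 1–5 |
|---|---|---|
| Cycle 1 safety labs and AE checks | Days 1, 3, 8 | Days 1, 3, 8, 15 |
| Longest gap, next labs on Day 22 | 22 − 8 = 14 days (14/21 = 67%) | 7 days (7/21 = 33%) |
| Longest run without a visit | Days 9–21 = 13 days (13/21 = 62%) | 6 days (6/21 = 29%) |
| All window days without a visit | 17 of 21 | 16 of 21 |

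If the +2-day window is used, the gap in Cohorts 6 and 7 is 15 or 16 days. The last row shows that the difference from the weekly cohorts is one visit, on Day 15.

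**2. Can later labs fall inside the window?** In Cohorts 6 and 7 they cannot, because Day 22 is the earliest. In Cohorts 1 to 5, Day 15 does. Their Cycle 2 Day 1 is nominally Day 22 too; the ±2-day window with the 6-day minimum between doses allows it as early as Day 15 + 6 = Day 21.

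**3. What the escalation rule requires.** Sections 4.9 and 5.1 ask for 21 days without a DLT. Neither requires a laboratory result after Day 8, and neither makes the decision wait for the Cycle 2 Day 1 result.

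**4. Illustration only.** Assume a laboratory event without symptoms that lasts L days, with onset uniform over the 21 days from Day 1 to Day 22. It is detected if a lab day falls within it. For L = 7, labs on Days 3 and 8 catch onsets from Day 1 to Day 8, which is 7/21.

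| Lab days | L = 7 | L = 5 |
|---|---|---|
| 3, 8 (Cohorts 6–7, in window) | 7/21 = 33% | 7/21 = 33% |
| 3, 8, 15 (Cohorts 1–5, in window) | 14/21 = 67% | 12/21 = 57% |
| 3, 8, 22 | 14/21 = 67% | 12/21 = 57% |
| 3, 8, 15, 22 | 21/21 = 100% | 17/21 = 81% |

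Counting whole days instead (onset on Days 1 to 21, L = 7), the first two rows become 8/21 = 38% and 15/21 = 71%. The documents support neither the duration nor the uniform onset.

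**5. Sampling passages side by side.**

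| Sample | Passages that include it | Passages that omit or exclude it for Cohorts 6–7 |
|---|---|---|
| Day 15 PK | 3.7.5, no cohort limit | Table 3.6-2 footnote k; 3.6 Day 15 visit not for these cohorts |
| Day 15 biomarkers | 3.7.6.1, no cohort limit | Table 3.6-2, no Day 15 column; 3.6 Day 15 visit not for these cohorts |
| 2- and 6-hour PK | 3.6 Cycle 1 Day 1 item 13, under an all-subjects heading | 3.7.5 and footnote k |

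For 2- and 6-hour biomarkers, item 13 and Section 3.7.6.1 agree. The exclusion in Section 3.7.5 is for PK alone.

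**6. Size of the PK consequence.** The protocol gives no half-life. Assume mono-exponential decline with half-lives of 3, 7, 14 and 21 days. A linear trapezoid from Day 8 to Day 22 then overstates the AUC of that segment by 75%, 15.5%, 4.0% and 1.8%. With a Day 15 sample the figures are 20.9%, 4.0%, 1.0% and 0.4%. A log-linear trapezoid has no such error under this assumption.

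**The case against.** A reader might infer that Days 9 to 21 are unobserved. They are not. Section 4.1.2 requires AE reporting throughout, Section 3.6 tells subjects to call between visits and attend if needed, Section 5.2 requires safety follow-up through the DLT period, and Section 4.9 item 5 requires treating investigators to summarize adverse events before a decision. This covers events with symptoms. It does not cover a silent laboratory change that no scheduled test would show.

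A reader might also infer that a Grade 3 or 4 result first seen on Day 22 is excluded as a DLT. Section 4.10 turns on when the toxicity occurs, not on when it is found, so an event shown to have begun by Day 21 still qualifies. For a laboratory value first seen on Day 22 the onset is unknown and the text does not settle the matter. Section 3.5.5 adds a real safeguard: Grade 3 or higher toxicity at least possibly related to the drug and seen in Cycle 2 or later suspends escalation for review. That result can therefore reach the escalation decision without being counted as a DLT. What remains is the event that arises and resolves within Days 9 to 21, and the absence of any rule that the decision awaits the Cycle 2 Day 1 result.

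Nor do the documents show that Day 15 sampling was intended for Cohorts 6 and 7. The Section 3.7 entries are timed to a Day 15 infusion these cohorts do not receive, so the wording may simply have been carried over from the weekly schedule. The Cycle 2 Day 1 pre-infusion sample also measures the end of the interval in subjects who reach Cycle 2; only the course between Day 8 and Day 22 is unmeasured.

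**Conclusion.** The point holds as a mismatch between schedule and window, together with internal contradictions. The 13 of 21 days and the 14-day laboratory gap follow from the protocol alone. The consequence is limited to silent Grade 3 or higher laboratory toxicity, which can be missed or left unclassified when Cohort 6 or 7 is declared DLT-free.

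The size of any undercount is not known. It is tempting to read the 33% against 67% as a measured bias against the weekly cohorts. The documents do not support that: the figures rest on an assumed 7-day silent event, and uniform onset ignores that weekly subjects are redosed on Days 8 and 15 while Cohorts 6 and 7 are not. To date Section 1.5 reports no DLT, and only Grade 1 or 2 events considered related, in the 17 subjects treated weekly.

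The conflicts over Day 15 samples and 2- and 6-hour PK draws need no assumption: sites cannot satisfy both versions.

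**What to change.** 1. Reconcile the Cohorts 6 and 7 schedule with the Section 4.10 window and the Section 4.9 decision, so that a safety laboratory result bearing on Days 9 to 21 is available and classified before a cohort is declared DLT-free. One way is to state how Cycle 2 Day 1 pre-dose results are treated and that the decision awaits them. A Day 15 laboratory visit is another option, though on its own it leaves Days 16 to 21 without a later in-window test. Because a DLT also ends dosing under Section 4.7 item 4, the sponsor's clinicians must settle the rule; this review proposes none.
2. Reconcile Table 3.6-2 and Section 3.6 Cycle 1 Day 1 item 13 with Sections 3.7.5 and 3.7.6.1: say whether Cohorts 6 and 7 have Day 15 PK and biomarker samples and 2- and 6-hour draws, and, for any Day 15 sample, give a time that does not refer to an infusion.

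The cost is wording and perhaps a day or so before the escalation decision. If the Day 15 option is chosen, it adds one outpatient blood draw in 6 to 12 subjects (3 to 6 in each of two cohorts).
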